10.2. Deaths, Serious Adverse Events and Other Significant Adverse Events

10.2.1. Deaths

All deaths, regardless of causality, will be provided in listings and written clinical narratives.

10.2.2. Serious Adverse Events

The number and percent of subjects with Treatment Emergent Serious Adverse Event (TESAE) will be displayed by system organ class and preferred term, and relationship to study drug. Within each preferred term, subjects will be counted only once if they had more than one TESAE event reported during the treatment period.

Clinical narratives for each TESAE observed will be written to include important data and safety findings related to the individual TESAE and included in the final clinical study report.

10.2.3. Adverse Events Leading to Discontinuation of Study Drug

The number and percent of subjects with TEAE's leading to discontinuation, or interruption, of study drug will be displayed by system organ class and preferred term. Within each preferred term, subjects will be counted only once if they had more than one TEAE leading to discontinuation, or interruption, of study drug reported during the treatment period.

A listing will be produced for all subjects who reported serious TEAEs or who discontinued study drug due to TEAEs.

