7 STUDY TREATMENTS

7.1 Treatments Administered

All subjects will begin treatment with AERT at 40 mg per day (2 x 20 mg) for 3 days, then increase to 60 mg per day (3 x 20 mg) for 3 days, and then increase to 80 mg per day (4 x 20 mg). Once the subject has reached the maintenance dose, they will remain on that dose for approximately 1 year (Figure 2). The maintenance dose will be the highest tolerated dose, not exceeding 80 mg per day. The description of study drug kits and treatments is shown below in Table 2. Subjects may choose to taper study drug after Visit 3 if they experience adverse events. Direct consultation with the investigator site must be conducted before consideration for dose taper. Dose tapers should occur over the course of 9 days in 20 mg increments. Subjects should be encouraged to titrate back to 80 mg once adverse events subside or remain on the maximally tolerated AERT dose. Up to 3 dose tapers over the course of the clinical study are permitted.

Table 2: Study Drug Kits and Treatments, Study OS440-3005

Dosage form description:	Blue, round biconvex tablets.
Package description:	HDPE white bottles with 60 active 20-mg tablets.
Daily dose:	40, 60, and 80 mg arbaclofen depending on the study day. There will be a 9-day titration period (3 days at 40 mg/day, 3 days at 60 mg/day, and then increase to 80 mg/day), then an approximately 1-year maintenance period at 80 mg/day or the highest tolerated dose, followed by a 2-week taper period. Study tablets will be taken twice daily (BID).
Cumulative maximal dosage:	up to 28,420 mg arbaclofen
Manufacturer:	Osmotica Pharmaceutical US LLC, Marietta, GA 30062

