7.4 Method of Assignment of Study Drug

[figure not shown]
This is an open-label study and all subjects will begin treatment with AERT at 40 mg per day (20 mg BID) for 3 days, then increase to 60 mg per day (20 mg in the morning and 2 x 20 mg in the evening) for 3 days, and then increase to 80 mg per day (2 x 20 mg BID). Once the subject has reached the maintenance dose, they will remain on that dose for approximately 1 year. The maintenance dose will be the highest tolerated dose, not exceeding 80 mg per day. Subject will be allowed to taper the 80-mg/day dose for issues of tolerability on at most three occasions. If tolerability issues persist, the subject will be required to discontinue from the study.

After Baseline procedures have been completed, authorized site personnel will acknowledge that the applicable subject met all the specified inclusion criteria ([Section 5.1](#)) and none of the exclusion criteria ([Section 5.2](#)) and an enrollment number will be sequentially assigned.

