11.5 Safety Endpoints

Safety endpoints will be reported on the Safety population. Subjects will be reported according to the treatment they actually received. Safety assessment will be based on descriptive statistics and individual subject listings. No statistical tests will be performed for any of the safety assessments.

All reported AEs will be mapped to the Medical Dictionary for Regulatory Activities (MedDRA) system organ classifications (SOCs) and preferred terms (PTs). If a subject reports multiple events of a single PT, the greatest severity and strongest investigator assessment of relationship to study treatment will be assigned to that PT. Should an event have a missing severity or relationship, it will be classified as having the highest severity and/or strongest relationship to study drug. Summaries of treatment-emergent AEs (TEAEs) will include any AEs reported beginning with the first dose of study treatment on Day 1. The occurrence of TEAEs will be summarized by treatment group using SOCs, PTs, and severity. Separate summaries of treatment-emergent SAEs, TEAEs considered related to study treatment, and events leading to the discontinuation of study drug will be generated.

Descriptive summaries of vital signs, clinical laboratory results, USP results, and the C-SSRS results will be presented by study visit and treatment group. The number and percentage of subjects with treatment-emergent clinical laboratory abnormalities will be summarized by treatment group. Normal range clinical laboratory shifts from baseline to end of study will be summarized by treatment group.

Concomitant medications will be coded using the World Health Organization (WHO) dictionary. These data will be summarized by treatment group. Previous and concomitant medications will be presented in a data listing.

Subject disposition will be presented for all subjects. The numbers of subjects who complete the study and who discontinue early from the study will be provided. The reasons for early discontinuation will also be presented.

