3.3. Summary of Statistical Analysis Changes to the Protocol

The analyses described in this analysis plan are consistent with the analyses described in the study protocol.

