8. SUMMARY OF STUDY DATA

8.1. Subject Disposition

A summary of the analysis sets includes the number and percentage of subjects screened (rollover and de novo) and in the safety population. All percentages will be based on the number of subjects screened.

End of trial information will also be summarized in this table, including the number of subjects completing the study and the number of subjects who prematurely discontinued the study with reasons for withdrawal. All percentages will be based on the number of subjects screened.

A by-subject data listing of study completion information including the reason for premature study withdrawal, if applicable, will be presented.

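### SAP 10.2.3 plans one table that, on its natural reading, pools adverse events leading to discontinuation with those leading only to interruption, whereas Protocol 11.5 specifies discontinuation on its own

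*SAP*

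**What the plan says.** - **SAP 10.2.3**, whose heading refers only to discontinuation of study drug, plans a display in which TEAEs "leading to discontinuation, or interruption, of study drug will be displayed by system organ class and preferred term". Its counting rule covers both actions together: within a preferred term, "subjects will be counted only once if they had more than one TEAE leading to discontinuation, or interruption, of study drug reported". It adds a by-subject listing that combines subjects with serious TEAEs and subjects who stopped study drug because of a TEAE.
- **Protocol 11.5** lists separate summaries of treatment-emergent SAEs, of treatment-related TEAEs, and of a third kind: "events leading to the discontinuation of study drug will be generated". Interruption is not mentioned.
- **SAP 3.3** declares no departure: "The analyses described in this analysis plan are consistent with the analyses described in the study protocol".
- **SAP 8.1** tabulates "the number of subjects who prematurely discontinued the study with reasons for withdrawal", with all percentages based on subjects screened.
- **Protocol 7.1 and 7.4** describe taper as a response to tolerability problems. Section 7.1 says "Subjects may choose to taper study drug after Visit 3 if they experience adverse events" and "Up to 3 dose tapers over the course of the clinical study are permitted". Section 7.4 says "Subject will be allowed to taper the 80-mg/day dose for issues of tolerability on at most three occasions" and requires discontinuation if the problems persist.

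**The concern.** A subject who paused study drug briefly because of an adverse event and a subject who stopped for good would fall in the same cell of the planned table. A reader who takes the section heading at face value would read the result as a discontinuation rate.

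Long-term tolerability is part of the primary objective (Protocol 3.1, SAP 4.1.1). The study has no control group, and SAP 7.4.1 plans no statistical tests, so the descriptive safety tables are the evidence. If the table of adverse events that made subjects stop treatment cannot be separated from those that made them pause, the summary specified in the protocol is missing from the report, and the SAP does not acknowledge the difference.

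**Working it through.** The documents state no discontinuation, interruption or dose-reduction rate, so there is no figure to reproduce. The check compares the texts and then shows what pooling does arithmetically.

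**1. Is the table pooled?** SAP 10.2.3 describes one display and gives one once-only counting rule covering both actions. It does not say that the actions will be shown in separate rows or tables. A programmer following the text would build one table. Two displays are conceivable but not specified.

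**2. Does this match the protocol?** Protocol 11.5 names discontinuation alone. SAP 10.2.3 names discontinuation or interruption. SAP 3.3 says nothing has changed. The difference is therefore undeclared.

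**3. Can interruption-only subjects occur?** Protocol 7.1.1 and 7.9 make discontinuation mandatory only when two conditions both hold: a run of at least 7 missed days, and less than 80% of doses taken in a 42-day period. A subject who misses 8 consecutive days and takes everything else has taken (42 − 8)/42 = 34/42 = 81%. The second condition is not met, so this rule does not require the subject to stop. A shorter pause does not meet the first condition. If an adverse event caused such a pause, the subject belongs in the pooled table without having discontinued.

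**4. What does pooling do to the rate?** Let *d* be the proportion of subjects with a TEAE leading to discontinuation, and *i* the proportion whose only such TEAEs led to interruption.

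- Pooled rate = *d* + *i*
- Ratio to the discontinuation rate = 1 + *i*/*d*

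The ratio is never below 1 and equals 1 only when *i* = 0. The same holds row by row for each preferred term. The table below uses assumed rates and N = 300, the approximate enrolment in Protocol 11.3 and SAP 6.

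| Assumed *d* | *i* = 0% | *i* = 2% | *i* = 5% | *i* = 10% |
|---|---|---|---|---|
| 5% (15 subjects) | 5% (15), ratio 1.0 | 7% (21), 1.4 | 10% (30), 2.0 | 15% (45), 3.0 |
| 10% (30) | 10% (30), 1.0 | 12% (36), 1.2 | 15% (45), 1.5 | 20% (60), 2.0 |
| 20% (60) | 20% (60), 1.0 | 22% (66), 1.1 | 25% (75), 1.25 | 30% (90), 1.5 |

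A discontinuation-only table would report *d* in every column.

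**5. Do other planned outputs supply the missing rate?**

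- Disposition (SAP 8.1) gives reasons for leaving the study, not for stopping drug. It has no breakdown by system organ class or preferred term, and its denominator is subjects screened rather than the Safety population.
- The listing in SAP 10.2.3 is restricted to serious events and discontinuations, so the individual cases can be found, but it gives no rates.
- Presentation by modal dose (SAP 7.4.1) and by dose at the time of the event (SAP 10.1) splits the table by dose, not by action taken.

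No planned table gives the discontinuation rate by system organ class and preferred term.

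**The case against.** The strongest reply is that this is a wording matter in a descriptive study. The sentence could be programmed as two displays, SAP 3.3 asserts consistency with the protocol, and no inference depends on the table. The protocol's response to tolerability problems is taper and then discontinuation rather than a pause, so interruption-only events may be few. The subjects who discontinued, and the events responsible, can be recovered from the listing, and adverse event is a defined withdrawal reason in Protocol 12.4.

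Much of this is fair. It limits what can be said about size, but it does not make the planned table match Protocol 11.5. A shared counting rule favours a single table, and counting from a listing does not replace a summary that the protocol specifies.

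A reader might be tempted by four stronger readings. The documents do not support them:

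- **That the discontinuation rate is inflated by a known factor.** No rates are given, and with no interruption-only events the ratio is 1.0. Only the direction is certain.
- **That dose reduction goes unmeasured.** SAP 8.6 summarizes and lists days at each dose level, SAP 7.4.1 presents tables by modal dose, and SAP 10.1 presents adverse events by dose at the time of the event. What is absent is a count of reductions attributed to adverse events and a table of the events that caused them.
- **That omitting a dose-reduction table departs from the protocol.** Protocol 11.5 does not promise one.
- **That discontinuation due to adverse events at 80 mg/day is the named key measure of tolerability.** Neither document names such a measure, and the primary objective states no dose. The 80 mg/day aim appears in the study rationale and the sample-size text.

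**Conclusion.** The point holds as a mismatch between SAP 10.2.3 and Protocol 11.5 that SAP 3.3 does not declare. On its natural reading, the SAP table reports discontinuation and interruption as one category, and no other planned table gives the discontinuation rate by system organ class and preferred term.

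The direction of the effect is certain: the pooled rate is at least the discontinuation rate and is higher if any interruption-only TEAE occurs. The magnitude cannot be determined from the documents. The range of 1.0 to 3.0 rests wholly on the assumed rates in the table and is not a prediction. The conclusion also assumes that the SAP sentence would be programmed as one table, which is the likelier reading but not an explicit instruction. It concerns reporting only, and no dosing or stopping rule is judged.

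**What to change.** In SAP 10.2.3:

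1. Present TEAEs leading to permanent discontinuation of study drug as their own table by system organ class and preferred term, on the Safety population, in line with Protocol 11.5.
2. Present TEAEs leading to interruption only in a separate table, and state how a subject with both outcomes for the same preferred term is counted.
3. With the split made, SAP 3.3 is accurate on this point. If a pooled table is kept as well, record it in SAP 3.3 as an addition to the protocol.

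Optional: if the collected data attribute dose changes to adverse events, add a table of TEAEs leading to dose reduction. Taper is the protocol's stated response to tolerability problems and is otherwise visible only indirectly.

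The cost is one extra table, or two with the optional one. The existing table and listing already require discontinuation and interruption to be identified, so the split needs no data that the SAP does not already presume. Whether dose reductions can be linked to specific events depends on the eCRF, which the documents do not show.

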10.3. Clinical Laboratory Evaluations

Clinical Laboratory results will be summarized descriptively by time point for the observed value as well as for the change from baseline value. In addition, laboratory shift tables will be provided for all laboratory parameters where low/normal/high or abnormal/normal status can be ascertained. Listings of individual laboratory parameters by visit with normal ranges and abnormality assessments will also be completed by subject.

10.4. Vital Signs

Vital sign results will be summarized descriptively by time point for the observed value as well as for the change from baseline value. All vital sign data by subject will be presented in a listing. Unscheduled visit results will not be summarized but will be included in subject data listings.

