9.2 Vital Signs

Vital signs will be measured at all visits. Blood pressure measurements will be made using a sphygmomanometer with an appropriate cuff size for the individual subject.

To evaluate the potential of arbaclofen to trigger orthostatic hypotension, BP and heart rate will be measured twice at each study visit. Orthostatic testing should take place in a quiet room, preferably at a temperature between 20°C and 24°C (68°F to 75°F). Emptying the bladder before testing is also recommended. The diagnosis of orthostatic hypotension is established by measuring the BP in the supine and then in the standing position, at least 3 minutes apart, and noting a substantial drop accompanied by symptoms of dizziness or syncope. A positive response is considered if systolic BP falls below 20 mmHg and diastolic BP 10 mmHg of baseline. If symptoms occur, the subject should be returned to the supine position immediately.

Vital signs, including BP, heart rate, respiratory rate, and body temperature, will be measured after the subject has been in a supine position quietly for 10 minutes. Then, with the subject in a standing position, BP and heart rate will be measured again after the supine assessment is completed.

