7.3. Management of Analysis Data

7.3.1. Data Handling

Unscheduled or repeated laboratory results will not be analyzed for the summary of continuous values but will be included in the laboratory shift tables as follows. Unscheduled tests will be included with the time of the nearest regularly scheduled test. If there is a scheduled test and one or more unscheduled tests assigned to the same time point, the most conservative test (i.e., a test with low or high results) will be used. Repeated tests will be included only if they reflect abnormal (low or high) results and the corresponding original results are normal. All laboratory values, for all visits, will be provided in by subject listings.

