7.4. Planned Study Analyses

7.4.1. Statistical Summaries: Descriptive and Inferential

No statistical tests will be performed in this study.

Descriptive summaries of variables will be provided where appropriate. For continuous variables, the number of non-missing values (n) and the median, mean, standard deviation, minimum, and maximum will be tabulated. For categorical variables, the counts and proportions of each value will be tabulated. Expansion of descriptive table categories may occur if such elaborations are thought to be useful.

For the summary statistics of all numerical variables unless otherwise specified, minimum and maximum will be displayed to the same level of precision as reported. Mean and median will be displayed to one level of precision greater than the data collected. The standard deviation / standard error will be displayed to two levels of precision greater than the data collected.

Change from baseline scores will be calculated as the post-baseline measurement minus the baseline value.

Unless otherwise specified, all tables will be presented by Modal Dose of 40 mg, 60 mg, 80 mg, and Overall group.

All collected data will be presented in listings. Data not subject to analysis according to this plan will not appear in any tables or figures but will be included in the data listings.

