10.6. Other Safety Measures

C-SSRS results will be presented in subject data listings.

USP summary scores (stress urinary incontinence score, overactive bladder score, and low stream score) will be summarized descriptively by time point for the observed value as well as for the change from baseline value. All USP data (including the 10 individual questions) will be presented in listings.

ECG parameters will be summarized descriptively by time point for the observed value as well as for the change from baseline value. All ECG data will be presented in listings.

No other safety analyses have been prospectively defined. If, however, after study results are reviewed, or the DSMB or Sponsor recommend additional safety parameters or analyses be completed, they will be fully described and documented in the final clinical study report. The SAP does not need to be amended to complete any other safety measures identified as post-hoc.

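### No planned table counts subjects with a notable vital-sign or ECG value, including the orthostatic response that the protocol takes paired blood pressures to detect

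*SAP*

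**What the plan says.** Vital signs and 12-lead ECGs are two of the six safety endpoints in SAP 4.2.1, in a study whose primary objective is long-term safety and tolerability.

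- **Vital signs, SAP 10.4:** "Vital sign results will be summarized descriptively by time point for the observed value as well as for the change from baseline value". For readings outside the schedule, "Unscheduled visit results will not be summarized but will be included in subject data listings".
- **ECG, SAP 10.6:** "ECG parameters will be summarized descriptively by time point for the observed value as well as for the change from baseline value", with all data listed. The section then states that "No other safety analyses have been prospectively defined".
- **Meaning of descriptive, SAP 7.4.1:** for continuous variables, "the number of non-missing values (n) and the median, mean, standard deviation, minimum, and maximum will be tabulated". Tables are by modal dose (40, 60, 80 mg) and overall. The same section adds that "Data not subject to analysis according to this plan will not appear in any tables or figures but will be included in the data listings".
- **Laboratory data, SAP 7.3.1:** "Unscheduled or repeated laboratory results will not be analyzed for the summary of continuous values but will be included in the laboratory shift tables". SAP 10.3 plans shift tables wherever an abnormal status can be determined, and protocol 11.5 plans the number and percentage of subjects with treatment-emergent laboratory abnormalities.
- **Purpose of the paired readings, protocol 9.2:** "To evaluate the potential of arbaclofen to trigger orthostatic hypotension, BP and heart rate will be measured twice at each study visit". That section goes on to define a positive response with figures of 20 mmHg systolic and 10 mmHg diastolic.

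**The concern.** Harm from blood pressure, heart rate or cardiac conduction usually appears as a marked change in a few people, not as a shift in the average. A safety reader wants to know how many subjects had such a value and at what dose. The planned tables do not answer that for either endpoint.

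The orthostatic question is the sharpest case. The protocol doubles the blood pressure and heart rate measurements at each visit for one stated reason and supplies a numerical criterion, and the analysis plan then never uses it. SAP 10.4 does not mention the supine-to-standing difference at all. The study report could list every reading and still not say how many subjects had a positive orthostatic response in a year on arbaclofen.

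**Working it through.** The plan states no figure to reproduce: protocol 11.3 gives no statistical rationale for the sample size and SAP 7.4.1 plans no tests. The check is a comparison of texts, followed by illustrative arithmetic. All rates, effect sizes, SDs and n = 200 below are assumptions.

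**1. Is a measured value counted anywhere?**

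| Data | By-visit descriptive | Count or shift table | Unscheduled results in a table | Rule making a value an AE |
|---|---|---|---|---|
| Laboratory | yes | yes (SAP 10.3, protocol 11.5) | yes, in shift tables (SAP 7.3.1) | yes (protocol 9.5) |
| USP score | yes | none planned | not stated | yes, 4-point increase (protocol 9.6.2) |
| Vital signs | yes | none | no (SAP 10.4) | none stated |
| ECG | yes | none | not stated | none stated |

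The remaining route is the TEAE tables in SAP 10.1, which depend on investigator reporting. In protocol 9.2 the diagnosis of orthostatic hypotension involves symptoms, whereas the positive response is given in mmHg. A symptomless fall could meet the second without being recorded as an AE.

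**2. Can the count be recovered from the planned tables?** Separate supine and standing summaries give the mean difference, if the same subjects contribute to both. They do not give the number with a fall of a given size. The minimum and maximum identify an extreme value, not how many subjects had one.

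**3. How far does a visit mean move?** Shift = fraction affected × size of change, for an extra systolic fall of 20 to 30 mmHg:
- 1%: 0.01 × 20 to 30 = 0.2 to 0.3 mmHg
- 2%: 0.02 × 20 to 30 = 0.4 to 0.6 mmHg
- 5%: 0.05 × 20 to 30 = 1.0 to 1.5 mmHg

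With n = 200 and an SD of change of 12 to 20 mmHg, the standard error is SD/√n = 12/√200 = 0.85 to 20/√200 = 1.41 mmHg. The 1% and 2% shifts lie inside one standard error.

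**4. Would by-visit percentages alone be enough?** Protocol Table 1 has six on-drug site visits with vital signs (Weeks 2, 6, 14, 28, 42, 54). With per-visit rate p, the share of subjects affected at any visit lies between p (always the same people) and 1 − (1 − p)^6 (independent visits):
- p = 1%: 1% to 1 − 0.99^6 = 5.9%, or 3 to 18 of 300
- p = 2%: 2% to 1 − 0.98^6 = 11.4%, or 6 to 34 of 300
- p = 5%: 5% to 1 − 0.95^6 = 26.5%, or 15 to 79 of 300

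Only a per-subject count separates these.

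**5. What would a count show?** The probability of at least one case is 1 − (1 − p)^N. At 1% incidence this is 0.95 for N = 300 (planned enrolment), 0.63 for N = 100 and 0.40 for N = 50 (the two exposure targets). With zero cases the one-sided 95% upper bound, 1 − 0.05^(1/N), is 1.0%, 3.0% and 5.8%.

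**6. Background in a worst-value count.** Suppose there is no drug effect and changes are normal. The chance of a fall of at least 30 mmHg at one visit is Φ(−30/12) = 0.6% to Φ(−30/20) = 6.7%. Over six independent visits it is 1 − (1 − 0.0062)^6 = 3.7% to 1 − (1 − 0.0668)^6 = 34%.

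**The case against.** Several points on the other side are sound.

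- **AE tables.** A reader might infer that notable values are never counted in any form. That goes too far. Protocol 9.7.1 has sites ask at each visit about changes in well-being, hospital admissions and accidents, and SAP 10.1 counts subjects with TEAEs by term, severity, period and dose. Subjects who felt ill are likely to appear there. The residual gap is values that no investigator reports as an AE.
- **Unscheduled readings.** A reader might reason from visit spacing. A 7-day episode meets one of six visits in 392 days with probability 6 × 7/392 = 11%, and a 14-day episode with 21%, so the rule would seem to lose 80% to 90% of episodes. The documents do not support that. The figure measures the visit schedule, not the effect of SAP 10.4, because a table can count only readings that were taken. Nothing says how many unscheduled readings will exist or why, and SAP 7.3.3 assigns early-termination readings to a scheduled visit. The exclusion is also stated only for vital signs; for ECGs the SAP is silent.
- **Extremes stay visible.** A very large change would appear in the tabulated minimum or maximum, by modal dose. This stands; only the number of subjects is missing.
- **No contradiction with the protocol.** Protocol 11.5 itself plans descriptive vital-sign summaries, and laboratory shift tables rest on normal ranges that are not supplied here for vital signs or ECG. This also stands, but protocol 9.2 does supply an orthostatic criterion.
- **Discretion.** SAP 7.4.1 allows table categories to be expanded and SAP 10.6 allows post-hoc safety analyses. Neither commits to a count, and a limit chosen later would be chosen with the data in view.
- **Background.** Step 6 shows that a worst-value percentage can be substantial without any drug effect. This limits what the count can prove and shapes the fix.

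**Conclusion.** The gap is real and cheap to close. As prospectively planned, neither vital signs nor ECGs have a table giving the number of subjects with a notable measured value. The protocol's own orthostatic question has a criterion and collected data but no planned answer. That conclusion rests on the text alone.

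The size can only be illustrated. At assumed rates of 1% to 2%, the visit mean moves by 0.2 to 0.6 mmHg, while the number of subjects affected at some on-drug visit could be anywhere from 3 to 34 of 300.

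The documents do not show that the safety conclusion is biased towards no effect. No test is planned, all values are listed, and reported AEs are counted. The ECG part is minor: a completer has one scheduled on-drug ECG, at Week 28, because the Week 60 recording follows the end of the taper at Week 56. One on-drug ECG is a limit of the design that a new table cannot repair.

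**What to change.** Keep the by-visit descriptive tables on scheduled values, and make these additions before database lock.

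1. **Reconcile the criterion.** Protocol 9.2 leaves unclear whether the reference is the supine reading or the Baseline visit, and whether the systolic and diastolic parts must both be met. The sponsor must settle this before anything is programmed.
2. **SAP 10.4, orthostatic count.** Give the number and percent of Safety Population subjects, by modal dose and overall, with any on-treatment reading (scheduled, unscheduled or early termination) that meets the reconciled criterion.
3. **SAP 10.4, other limits.** Give the same count for any further vital-sign limits the sponsor fixes in advance. Handle unscheduled values as SAP 7.3.1 does for laboratory tests: out of the means, into the categorical table.
4. **Context for background.** Show the same counts at Baseline and at each scheduled visit beside the any-time count.
5. **SAP 10.6, optional.** Add a similar categorical count for ECG with sponsor-set limits, and state how unscheduled ECGs are handled.

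The cost is SAP wording and a few tables from data already being collected, plus the sponsor's decision on limits. The downside is that any-time percentages include background variation and exceed single-visit ones. With no control group they describe what was observed and cannot be attributed to the drug; the table footnotes should say so.
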